5.3.2. Photographing the Wound

In order to obtain an accurate assessment of the wound, photographs of the wound and surrounding skin must be obtained using the eKare inSight® wound assessment camera. Photographs taken with the eKare device will include a visible label containing the following information subject number and date.

5.3.3. Secondary Dressing Notation

All wounds following treatment will be covered with a suitable secondary dressing where Investigators judge that a wound dressing with debridement or moisture control will be appropriate. The secondary dressings used will be noted during each visit. Medline Industries, Inc. will provide Optifoam® Gentle Super Absorbent silicone dressings for use as secondary dressings.

5.3.4. Debridement

Mechanical debridement should only be performed per normal standard of care. If mechanical debridement occurs at a visit, it will be noted on the CRF.

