5.3.1. Wound Evaluation

Wound evaluation for data collection purposes will begin at the initial visit and thereafter during each visit at the outpatient centers where this study is going to be conducted. Wound Evaluation will include the following parameters (please also see sample Case Report Form (CRF) in Appendix D which will be used at each visit):

- Wound size (length, width and depth)
- Evaluation of Odor. Investigator assessment of wound odor will be captured via a 4-point categorical scale after each application.
- Percent of Necrotic Tissue. The percent of necrotic tissue will be assessed based on photos taken of the wound with eKare inSight® and visual confirmation from the Investigator to determine the percent covered with the necrotic tissue versus the total area of the wound. This will be entered in question six of the Bates-Jensen Wound Assessment Tool, as described in Appendix C.
- Pain Assessments. Pain will be assessed by the subject after the application (or re-application, for interim visits) of the dressing. Pain will be based on a 10-point Pain Score.
- Site Infections. Any infections at the wound site will be documented. In the event a participant develops an infection his/her participation in the study will discontinue, and the physician will implement appropriate treatment measurements.
- Bates-Jensen Wound Assessment Tool (BWAT). The BWAT will be administered to further characterize the wound. Please see Appendix C for BWAT.

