5.4.1. Data collection

All activities listed in section 5.3.1 and 5.3.2 will take place in the Final Visit in order to complete data collection. Notations on dressings and debridement will not be documented at this visit, though they may of course occur based on an Investigator's judgment.

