5.4.2. Physician Questionnaire

Product ease of use will be evaluated using on the Investigator Questionnaire (Appendix E) at the end of subject's study participation.

TABLE 5.1 TIME AND EVENTS SCHEDULE

REQUIRED ASSESSMENTS	SCREENING VISIT Day 0 (May be combined with first interim visit, Day 1)	INITIAL VISIT Day 1	INTERIM VISITS Approx. Every 7 Days	FINAL VISIT ⁵ Approx. 28 days after Day 1 visit
Informed Consent	X			
Demographics	X			
Medical History	X			
Concomitant Medication	X			
Physical Examination	X			
Doppler Assessment	X ^{1,3}			
Blood Glucose Assessment	X ^{1,2,4}			
Wound Screening Evaluation	X			
Confirmation of Eligibility	X	X	X	
Adverse Event Assessment	X	X	X	X
Wound Evaluation		X	X	X
Wound Photograph		X	X	X
TheraHoney® Foam Flex		X	X	
Secondary Dressing Notation		X ¹	X ¹	
Mechanical debridement noted		X ¹	X ¹	
Investigator Questionnaire				X

¹If required

²Within 30 days of screening visit or at screening visit

³Within 90 days of screening visit or at screening visit

⁴Diabetic subjects only

⁵Final visit may be an interim visit in the event patient heals fully before 4 weeks and no longer requires treatment

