8.2. SAMPLE SIZE JUSTIFICATION

This is an observational study without a comparison group; therefore a formal power analysis is not feasible. Rather, the study will aim to collect data from 20 patients with evaluable data. The key analysis for the study is providing a quantitative estimate of debridement of necrotic tissue. To this end, a 95% confidence interval centered on the sample mean for necrotic tissue reduction will be created using the critical t value for this analysis; this will provide the best point estimate for debridement, as well as a measure of uncertainty, which will takes the sample size into account.

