10.4 APPENDIX D: Case Report Form

Case Report Form (R16-017)

Subject Number:	Visit Date:	Visit Time:	AM	PM	Visit Type and Number:	
Height (inches):	Weight (lbs):	Age:				
Sex:  Male	 Female					
Race:  White	 Black	 Hispanic or Latino	 Asian	 Other/Mixed Race	 Native American	
Was mechanical debridement used?  Yes		 No				
Was a secondary dressing used?  Yes		 No	If yes, what kind? _____			
Wound Assessment						
Physical Examination and Wound Zoom Analysis			Bates – Jensen Wound Assessment Tool (BWAT)			

Diagnosis: _____
 
What is the percent of necrotic tissue? _____ %
 
Wound size (cm): Width _____ x Length _____ x Depth _____
 
Evaluation of odor: _____
 
 1  2  3  4
 
VAS Pain scale score within 10 minutes following dressing change: _____
 
 0  1  2  3  4  5  6  7  8  9  10
 
Site Infection: Yes No
 
If yes, discontinue subject and note steps taken:
			
1. Skin: _____
 
2. Depth: _____
 
3. Edges: _____
 
4. Undermining: _____
 
5. Necrotic Tissue Type: _____
 
6. Necrotic Tissue Amount: _____
 
7. Exudate Type: _____
 
8. Exudate Amount: _____
 
9. Skin Color Surrounding Wound: _____
 
10. Peripheral Tissue Edema: _____
 
11. Peripheral Tissue Induration: _____
 
12. Granulation Tissue: _____
 
13. Epithelialization: _____
 
TOTAL BWAT SCORE: _____
			

Place photograph of the wound from the Wound Zoom camera below:

Subject #: _____ **Date:** _____

*Please note that the information in the picture should match the above information.

Signature _____ **Date** _____

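### Mechanical debridement removes the tissue the primary endpoint scores and is recorded on the CRF, but the analysis never uses the record, so the measured reduction mixes it with the dressing's effect

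*Combined protocol and SAP*

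**What the plan says.** - **Objective and mechanism.** Section 3.1 asks about the dressing's ability to remove necrotic tissue. Section 2.1 describes dressings of this kind as acting by autolytic debridement.
- **What is allowed and recorded.** Section 5.3.4: "Mechanical debridement should only be performed per normal standard of care", and "If mechanical debridement occurs at a visit, it will be noted on the CRF". The Appendix D form has a Yes/No item, "Was mechanical debridement used".
- **Final Visit.** Section 5.4.1: "Notations on dressings and debridement will not be documented at this visit", while granting that debridement may occur then. The Table 5.1 row "Mechanical debridement noted" is marked for the Initial and Interim Visits only.
- **Analysis.** Section 8.2: "The key analysis for the study is providing a quantitative estimate of debridement of necrotic tissue". Debridement there means the outcome, not the procedure. Section 8.3.1 forms a 95% interval for mean reduction and treats a positive lower bound as significant reduction. Section 8.3.3 requires only valid Day 1 and Final Visit necrotic tissue values. Section 8.3.2 lists no debridement variable, and 8.4 covers withdrawals and adverse events.

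**The concern.** Mechanical debridement acts directly on the quantity being scored. If it happens after the Day 1 score and before the Final Visit score, the tissue removed is part of the reduction, whatever the dressing did. Nothing in 8.2 to 8.4 excludes, stratifies by, adjusts for or tabulates subjects who were debrided. The criterion could be met through debridement alone, and a reader of the report could not tell how many subjects behind the interval had been debrided.

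Two gaps in procedure add to this. No section says whether the photograph and score come before debridement at a visit. And because Final Visit debridement is not documented, debridement just before the last score could enter the endpoint with no trace.

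**Working it through.** **No figure to reproduce.** Section 8.2 gives 20 evaluable subjects with no effect size, SD or target width. The checks below apply the plan's own rule, a two-sided 95% t interval with success if the lower bound exceeds zero. They set the dressing effect to zero. Debridement frequency, amount removed and SD are not in the documents and are assumed.

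**Step 1: category scale of 8.3.1.** Inputs: n = 20, t(0.975, 19) = 2.093. Suppose k subjects drop one category and nobody else changes. Then mean = k/20, SD = √[20·p(1−p)/19] with p = k/20, and the interval is mean ± 2.093·SD/√20.

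| k | Mean | SD | Half-width | 95% CI | Criterion met? |
|---|---|---|---|---|---|
| 3 | 0.15 | 0.366 | 0.171 | -0.021 to 0.321 | No |
| 4 | 0.20 | 0.410 | 0.192 | +0.008 to 0.392 | Yes |

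**Step 2: crossings are not the same as debridements.** Assume baseline is uniform from 20% to 100%, because 4.2.1 admits wounds from 20%. The 8.3.1 categories break above 0, 25, 50 and 75.
- Removing 10 points changes the category for whole-percent baselines 26–35, 51–60 and 76–85: 30 of 81 values, about 37%.
- Removing 20 points does so for 26–45, 51–70, 76–95 and for 20 itself: 61 of 81, about 75%.

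So the four in Step 1 are four boundary crossings. More than four debridements could be needed to produce them.

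**Step 3: percentage scale (the Appendix D percent field).** Simulated trials with n = 20. Final value = baseline − removal + normal error (SD 20 or 30), bounded to 0–100. Removal = min(D, baseline) for a random share f of subjects, otherwise zero. Reduction = baseline − final value.

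| Share debrided | Points removed | Chance of a positive lower bound |
|---|---|---|
| 0 | 0 | about 4% (SD 20) to 5% (SD 30) |
| 10% | 10 | about 6% |
| 75% | 30 | about 98% (SD 20; about 86% at SD 30) |

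The no-debridement rate exceeds the nominal 2.5% because bounding cuts off more upward error near 100% than downward error near 0%. The excess due to debridement should therefore be judged against 4–5%.

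**Step 4: direction.** Debridement after the Day 1 score and before the final score raises the measured reduction. Debridement before the Day 1 score would work the other way, by lowering the baseline. No size is claimed for that. The main bias against objective 3.1 is upward.

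**The case against.** **An uncontrolled study cannot attribute an effect anyway.** Section 8.2 says there is no comparison group, section 2.4 puts comparison with other therapies out of scope, and natural change and offloading also enter the interval. This stands, and much of the defect is an undefined estimand. Debridement still differs from other background care: it removes the scored tissue directly, and the study already collects the variable needed to describe it.

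**The plan does not claim the reduction for the dressing.** A reader might infer that 8.3.1 does. It names only a significant reduction in necrotic tissue. The link to the dressing comes from objective 3.1.

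**The Final Visit provisions contradict each other.** A reader might infer this because 5.4.1 says "All activities listed in section 5.3.1 and 5.3.2 will take place in the Final Visit" and 5.3.1 refers to the sample form "in Appendix D which will be used at each visit", which carries the debridement item. But 5.4.1 repeats only 5.3.1 and 5.3.2, debridement sits in 5.3.4, and 5.4.1 with Table 5.1 makes an explicit exception. This is a recording gap, and it reaches the endpoint only if debridement precedes scoring.

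**Scoring comes first because wound evaluation is listed first.** The section order does not establish that. Section 5.3.1 itself includes pain and odor assessed after dressing application, so it is not chronological.

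**Other safeguards exist.** The 4.2.2 exclusion for treatment that may affect the outcome covers only treatment before enrollment. Appendix E asks the investigator whether the product helped promote autolytic debridement, but that is a subjective opinion outside the analysis plan. Neither closes the gap.

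**Conclusion.** The concern holds. Under the plan as written, mechanically removed tissue counts toward a reduction that objective 3.1 ties to the dressing, and the available record is unused. The change should be made.

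The numbers show mechanism only. Four one-category crossings among 20 subjects meet the criterion and three do not, assuming no dressing effect and no other change. On a bounded percentage scale with SD 20–30, the chance of a positive lower bound runs from about 6% to about 98% over the assumed range, against 4–5% with no debridement. A reader might infer that the bias is probably large, or that four debrided subjects are enough. The documents support neither: they give no frequency or amount of debridement, and a debridement need not cross a category boundary.

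**What to change.** 1. **5.3.1 and 5.3.2:** state that at every visit, including the Final Visit, the photograph and percent necrotic tissue are taken before any debridement done at that visit.
2. **5.4.1 and Table 5.1:** keep the existing CRF debridement item at the Final Visit.
3. **8.3:** describe the primary estimate as reduction under the dressing plus standard care, including any mechanical debridement. Under that description debridement is part of the estimate. Report the number debrided by visit, and the mean reduction with 95% CI by debridement status. These groups are descriptive, since wounds still necrotic are plausibly the ones debrided.
4. **8.3:** add one prespecified sensitivity analysis on the same scale as the primary. For subjects debrided after Day 1, use the last value scored before the first such debridement. Subjects debrided on Day 1 have no later value free of debridement, so report them separately. State the n, the shorter follow-up (about 7 of 28 days if debridement is at the first interim visit) and that truncation may be informative.

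Attribute neither the primary nor the sensitivity interval to the dressing alone.

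**Cost.** A few sentences, one table cell and a little more analysis, with no new measurement. The sensitivity interval is less precise. Its half-width is t/√n in SD units: 2.093/√20 = 0.47 at n = 20, 2.145/√15 = 0.55 at n = 15 and 2.262/√10 = 0.72 at n = 10, where 15 and 10 are assumed numbers left after Day 1 debridement. Whether and when debridement is clinically performed does not change.

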5.3.5. TheraHoney® Foam Flex Application

The application of TheraHoney® Foam Flex will be performed according to the product labeling during the Initial Visit (Day 1) and subsequent Interim Visits. Dressing changes will take place daily, with the Investigator instructing participants on how to change the dressing at home on days when they do not visit the clinic. The use of secondary dressings will also be done at the discretion of an Investigator. At the discretion of an Investigator, use of TheraHoney® Foam Flex should be discontinued due to adverse events or lack of wound closure response.

5.4. FINAL VISIT

The Final Visit will be scheduled to take place approximately 4 weeks following the Initial Visit. In the event that during a weekly Interim Visit, an Investigator judges the wound to be 100% healed and medical care is no longer necessary, that Interim Visit will be deemed the Final Visit.

5.4.1. Data collection

All activities listed in section 5.3.1 and 5.3.2 will take place in the Final Visit in order to complete data collection. Notations on dressings and debridement will not be documented at this visit, though they may of course occur based on an Investigator's judgment.

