8.3. ANALYSIS OF EFFICACY DATA

8.3.1. Primary Endpoint

Percent reduction in necrotic tissue will serve as the primary endpoint. The Investigator will analyze wound photographs and visually inspect the wound in order to calculate percent necrotic tissue and enter a value of 1-5, corresponding to:

- 1 = No necrotic tissue
- 2 = 0% - 25%
- 3 = 26% - 50%
- 4 = 51% - 75%
- 5 = 76% - 100%

The 95% confidence interval for the mean reduction in necrotic tissue across the study period will be evaluated to determine if the lower bound is positive, which would be an indication of significant reduction in necrotic tissue.

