8.3.3. Evaluable Dataset

An evaluable dataset will be used to conduct the efficacy assessments. This dataset will be defined as subjects who have at least a valid measurement for necrotic tissue from the Day 1 visit and their Final Visit, given that this will make up the measurement of the primary endpoint.

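### Debridement at the Final Visit is exempt from documentation and no section puts the necrosis score before it, so hand removal could count as product effect unseen in the study data

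*Combined protocol and SAP*

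**What the plan says.** Section 5.4.1 carries the wound evaluation (5.3.1) and photography (5.3.2) over to the Final Visit, and then states: "Notations on dressings and debridement will not be documented at this visit, though they may of course occur". Table 5.1 matches this. Its row "Mechanical debridement noted" is marked, if required, for the Initial and Interim Visits and is empty for the Final Visit.

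For the Initial and Interim Visits, section 5.3.4 permits mechanical debridement under standard of care and adds: "If mechanical debridement occurs at a visit, it will be noted on the CRF". The form in Appendix D has one yes/no item, "Was mechanical debridement used", with no field for type or for timing relative to the score. Section 5.3.1 describes this as the "Case Report Form (CRF) in Appendix D which will be used at each visit".

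On the endpoint, section 8.3.1 says "Percent reduction in necrotic tissue will serve as the primary endpoint", with the Investigator entering a category from 1 to 5. The 95% interval for the mean reduction is then "evaluated to determine if the lower bound is positive". Section 8.3.3 requires of each evaluable subject "at least a valid measurement for necrotic tissue from the Day 1 visit and their Final Visit".

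**The concern.** The study asks whether a dressing removes necrotic tissue. Removal by hand is the most direct rival explanation for a lower necrosis score. The design offers little to separate the two: it is single-arm and open-label, and the Investigator scores the wound.

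Two features combine at the visit that closes the primary endpoint. The protocol foresees debridement there but exempts it from documentation. It also does not fix the order of photograph, score and debridement within a visit. If debridement came first, the lower score would enter the primary change as if the dressing had produced it, and the planned data would hold no entry to reveal this. A later analysis could not recover the information from the case report form.

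The exemption also fits poorly with section 5.3.1. The Appendix D form, with its debridement box, is to be used at every visit, yet section 5.4.1 says that the item is not documented at the last one. A blank or a No on the Final Visit form could then mean either that nothing was done or that nothing was recorded.

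**Working it through.** **Reading the sections together**

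- Recording: Day 1 and Interim Visits, yes, for mechanical debridement (5.3.4, Table 5.1, Appendix D). Final Visit, no (5.4.1, Table 5.1).
- Order within a visit: not stated in 5.3.1, 5.3.2, 5.3.4, 5.4.1 or 8.3.1.
- Endpoint values: Day 1 and Final Visit (8.3.3).
- Form: printed with a debridement box and used at each visit (5.3.1, Appendix D), against the exemption in 5.4.1.

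**What scoring order could do to the success rule**

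The plan gives no SD, effect size or power, so there is no figure of its own to reproduce. The following is an illustration. Its inputs from the documents are n = 20 evaluable subjects and a t interval for the mean (section 8.2), with success if the lower bound is above zero (8.3.1). The assumptions are that reduction is counted in bands of the 1-5 scale, that k subjects drop one band only because they were debrided before the final score, and that the other 20 - k do not change.

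Mean = k/20. SD = sqrt[20 × p × (1 - p) / 19] with p = k/20. Lower bound = mean - t × SD / sqrt(20), with t on 19 degrees of freedom = 2.093.

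- k = 4: mean 0.20; SD = sqrt(3.20/19) = 0.410; lower bound = 0.20 - 2.093 × 0.410/4.472 = 0.20 - 0.192 = **+0.008**. The rule is met.
- k = 3: mean 0.15; SD = sqrt(2.55/19) = 0.366; lower bound = 0.15 - 0.171 = **-0.021**. The rule is not met.

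Mean and SD scale together with the size of the drop, so the threshold stays at four for larger equal drops: with k = 4 the lower bound is +0.016 for two bands and +0.024 for three.

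Zero change in everyone else is artificial. A second version therefore gave all subjects normal noise with mean zero (no true effect), added a one-band drop in k subjects, and simulated 100,000 trials per setting. The chance of a positive lower bound was:

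| Assumed SD (bands) | k = 0 | k = 4 |
|---|---|---|
| 0.5 | 2.5% | 20.5% |
| 0.8 | 2.5% | 12.9% |
| 1.0 | 2.5% | 10.4% |

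**The case against.** The strongest reply is that section 5.4.1 first completes data collection and only then mentions debridement, so it most naturally describes ordinary care after the score. Debridement done at that point cannot affect the endpoint. This is a fair reading, and the documents do not support the inference that final scores will be taken after debridement. But the order is nowhere stated, so the reading is not secured either.

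Four other stronger readings are tempting and do not hold:

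- That 5.3.4 contradicts 5.4.1. Section 5.3.4 sits under the heading for the Initial and Interim Visits, so the two agree. The real tension is between 5.4.1 and the use of the Appendix D form at each visit.
- That every subject debrided at the Final Visit would look undebrided. Anyone mechanically debrided earlier is already flagged. The gap concerns those debrided only at the end, and the Final Visit event itself.
- That debridement would leave no trace anywhere. The clinic chart may show it. Section 5.2.3 also asks for ongoing adjunct wound therapies and could catch some non-mechanical methods. Because mechanical is undefined, it may even be meant to cover all hands-on removal. What is missing is an entry in the planned study data.
- That +0.008 estimates the bias. The count of four is assumed, and zero change in the others is a special case. The calculation also measures the effect of scoring order: recording alone would not move the bound.

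It is also true that section 8.3 makes no use of the debridement record, so the missing entry alters no planned analysis. That does not answer the point, since data never collected cannot be used later.

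**Conclusion.** The point stands as a possible bias with a firm documentary basis. The exemption is a stated rule, not an omission of detail. It applies at the visit that supplies the second value of the primary endpoint, and nothing places the score before debridement. Sections 5.3.1 and 5.4.1 and Appendix D must be reconciled.

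The size is conditional. The documents give neither the frequency of Final Visit debridement nor the SD of change. Under the assumptions shown, as few as four subjects in 20 could carry the result over the success threshold if no one else changed. With realistic scatter and no true effect, the same four would raise the false-success chance roughly four- to eightfold (10.4/2.5 to 20.5/2.5). If every score in fact precedes debridement at that visit, this bias is zero. The change is worth making because it is nearly free and the information cannot be rebuilt from the form afterwards.

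**What to change.** 1. In section 5.3.1, state that at every visit, including Day 1 and the Final Visit, the photograph and the necrosis score are completed before any debridement performed at that visit. This is the step that protects the endpoint.
2. In section 5.4.1 and Table 5.1, remove the debridement exemption so that debridement is recorded at the Final Visit as at the others. The exemption for dressing notation may stay. This also resolves the tension with the use of the Appendix D form at each visit.
3. In Appendix D, widen the item to any debridement, with its type and whether it took place before or after scoring.

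Whether and how to debride stays with the Investigator, and no wound preparation step is added. The cost is a few lines of text, one mark in Table 5.1 and one line on the form.
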